8.10 Correlative Analysis

c-Met and EGFR levels as quantitated by RT-qPCR will be compared to c-Met and EGFR biomarkers as determined by IHC using Bland-Altman plots and intra-class correlation measures. All biomarkers, both pre-treatment and changes over time will be correlated with PFS using Cox proportional hazards regression. Time dependent ROC curves will be generated to assess predictive ability.

CONFIDENTIAL

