5 STUDY POPULATION

5.1 Inclusion Criteria

A subject must fully meet all of the following criteria to be eligible for the study:

1. The subject has a biopsy-proven diagnosis of adenocarcinoma of the pancreas (or recurrence of previously resected disease) with metastatic disease that is measurable per RECIST 1.1;
2. The subject must have an archived tissue sample such as a prior surgical sample or biopsy sample that is adequate for testing;
3. The subject must have EGFR and c-Met overexpressed in tumor as determined by immunohistochemistry (IHC) test score of 2+ for both markers;
4. The subject has demonstrated radiographic progression after front-line treatment (prior adjuvant therapy allowed if ≥ 6 months elapsed between end of adjuvant therapy and metastatic relapse);
5. The subject is ≥ 18 years old on the day of consent;
6. The subject has an Eastern Cooperative Oncology Group (ECOG) performance status of 0 or 1;
7. The subject has recovery to baseline or \leq Grade 1 CTCAE v.4.03 from toxicities related to any prior treatments, unless AE(s) are clinically nonsignificant and/or stable on supportive therapy;
8. The subject has organ and marrow function and laboratory values as follows within 7 days before the first dose of study treatment:
 - a. The ANC $\geq 1500/\text{mm}^3$ without colony stimulating factor support;
 - b. Platelets $\geq 100,000/\text{mm}^3$;
 - c. Hemoglobin ≥ 9 g/dL;
 - d. Bilirubin $\leq 1.5 \times$ the ULN. For subjects with known Gilbert's disease, bilirubin ≤ 3.0 mg/dL;

CONFIDENTIAL

- e. $AST/ALT \leq 3 \times$ the ULN;
 - f. Serum albumin ≥ 2.8 g/dl;
 - g. Serum creatinine $\leq 1.5 \times$ the ULN or creatinine clearance (CrCl) ≥ 40 mL/min. For creatinine clearance estimation, the Cockcroft and Gault equation should be used:
 - i. Male: $CrCl \text{ (mL/min)} = (140 - \text{age}) \times \text{wt (kg)} / (\text{serum creatinine} \times 72)$;
 - ii. Female: Multiply above result by 0.85;
 - h. UPCR ≤ 1 ;
 - i. Serum phosphorus, calcium, magnesium and potassium \geq LLN;
 - j. Prothrombin time (PT)/INR or partial thromboplastin time (PTT) test $< 1.3 \times$ the ULN *within 7 days* before the first dose of study treatment;
9. The subject is capable of understanding and complying with the protocol requirements and has signed the informed consent document;
10. The subject has a life expectancy of 12 weeks or greater;
11. The subject is able to tolerate oral medications and no evidence of ongoing malabsorption;

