6.6 Correlative Studies

HGF and its receptor, c-Met (also known as Met and MET), are also overexpressed in PDAC. c-Met also heterodimerizes with EGFR, and EGFR-Met cross-talk may contribute to chemoresistance. Np-1 and Np-2, which are transmembrane proteins that act as co-receptors for VEGF-A, HGF, and class 3–secreted semaphorins, are also overexpressed in PDAC, and Np-1 associates with Met, enhancing HGF's ability to promote migration and invasion in pancreatic cancer cells (PCCs), as previously reported by us. Np-1, which does not associate with EGFR, can signal via integrin beta 1 (ITG- β 1) to promote PCC invasion and survival. ITG- β 1, which is also overexpressed in PDAC, can enhance EGFR signaling. Together, these observations point to a previously unrecognized signaling node in PDAC that consists of Met/EGFR/Np-1/2, and ITG- β 1. In this proposal, we will test the hypothesis that it is possible to target this signaling node by dual inhibition of Met with cabozantinib and EGFR with erlotinib.

CONFIDENTIAL

Based on the above, we will analyze tumor tissue to assess expression of c-Met and EGFR by RT-qPCR and immunohistochemistry. Immunostaining will be conducted by Indiana University Health Department of Pathology on baseline samples and in the [name] laboratory for samples collected post-treatment using the same standard operating procedures (SOPs). SOPs will include same antibodies and antibody titers, and same antigen exposure procedures. The advantages of using the RT-qPCR and immunohistochemistry approaches is that they are easy to execute rapidly and may yield important information for trial design and interpretation. By rapidly performing RT-qPCR for HGF, c-Met, and EGFR, we will be able to accurately evaluate which PDAC samples express high levels of all three transcripts, and consider these patients as candidate for the clinical trial, even before performing the more sophisticated studies on the tumors as outlined above. In addition, we will assess expression of Np-1, ITG-b1, p-EGFR and p-c-Met by immunostaining and/or immunofluorescence.

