We will perform contrast enhanced CT or MRI every 8 weeks with additional correlative studies on blood and tissue collected at baseline (pre-treatment) and Cycle 1/Day 15 (post-treatment) to measure Met and EGFR mRNA by qPCR, blood collection to assay plasma HGF and soluble Met receptor, and to evaluate Met and EGFR total phosphoprotein levels by electro-luminescent 2-site immunoassays in tissue to determine if these assays can serve as predictors of response to therapy.

All patients must have archival tissue for EGFR and c-Met expression testing by immunohistochemistry (IHC) as only patients with a test score of 2+ for both markers will be eligible to participate in this trial. Patients will be asked for archival tissue during the screening period (i.e. at baseline). It is anticipated that most patients who may be eligible for this study will have archival tissue available for screening. Patients without archival tissue are ineligible. Tumor tissue is required pre-treatment as part of study eligibility criteria to test for EGFR and c-MET expression. KRAS will also be tested if previous KRAS testing was not done or results are unknown AND there is adequate tissue available from tissue collected at screening. Archival tissue obtained may come from previous EUS or CT-guided biopsies or surgical resection. FNA cores are acceptable. Primary lesion tissue (typically obtained via EUS-guided biopsy or surgical resection) is preferred; however, metastatic lesion tissue may also be used (typically obtained via CT-guided biopsy). Only samples collected from eligible patients during the screening period will be utilized for the correlative studies which are outlined in this trial. Tissue samples collected from ineligible patients during screening will be discarded.

CONFIDENTIAL

Approximately 20 ml of blood will be collected at baseline (during screening period or prior to first administration of study drug on Cycle 1/Day 1) and beginning Cycle 1/Day 15 and every 4 weeks thereafter (i.e. Cycle 2/Day 1, Cycle 3/Day 1, Cycle 4/Day 1, etc.). Only samples collected from eligible patients during the screening period will be utilized for the correlative studies which are outlined in this trial. Blood samples collected from ineligible patients during screening will be discarded.

Complete details regarding tissue and blood collection, processing, transfer and storage information for these correlative studies can be found in the Laboratory Manual for this study.

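### Section 8.10 compares RT-qPCR with IHC only in patients selected on the IHC score, so agreement across the expression range cannot be assessed

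*Combined protocol and SAP*

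**What the plan says.** Section 8.10 plans this comparison: "c-Met and EGFR levels as quantitated by RT-qPCR will be compared to c-Met and EGFR biomarkers as determined by IHC". The methods it names are the intra-class correlation and the Bland-Altman plot. It gives no analysis set, no IHC scale and no target precision.

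Three other provisions decide who is in that comparison:

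- **Entry (5.1, criterion 3):** "EGFR and c-Met overexpressed in tumor as determined by immunohistochemistry (IHC) test score of 2+ for both markers". Section 6.6 repeats the threshold. Neither place says whether 2+ is exact or a minimum, and no H-score or percent-positive measure is defined.
- **Samples used (6.6):** "Only samples collected from eligible patients during the screening period will be utilized for the correlative studies which are outlined in this trial".
- **Samples not used (6.6, and footnote 8 of the schedule in 6.1):** "Tissue samples collected from ineligible patients during screening will be discarded".

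Section 6.6 also describes RT-qPCR as a quick way to find trial candidates: "By rapidly performing RT-qPCR for HGF, c-Met, and EGFR, we will be able to accurately evaluate which PDAC samples" have high transcript levels. That implies assaying some patients before their eligibility is known.

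**The concern.** Judging whether two assays agree needs tumors that are low, intermediate and high on both. Here the enrolled group is defined by one of the two assays, and the samples that would supply the low end are barred from the correlative work. This does not depend on the statistic chosen: a rank correlation meets the same restriction as the intra-class correlation.

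The rationale (2.2) quotes co-overexpression of 3% from TCGA and about 30% from the group's own unpublished RT-qPCR work, while eligibility rests on IHC. Section 8.10 is the only planned analysis that links RT-qPCR to IHC. A weak result there could be read as poor agreement between the assays when it partly reflects the selection.

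**Working it through.** **Number of patients available.** Section 8.10 has no figure of its own, so the design in 8.5 sets n. With 0 of 11 as the stopping rule and p = 0.025:

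- Early termination: 0.975^11 = 0.757, as stated.
- Expected size: 11 + 26 × (1 − 0.757) = 17.32, as stated.
- Exact error rates are 0.0447 and 0.1981, matching the stated 0.045 and 0.198.

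The comparison therefore has 37 patients (at most 40) if the trial continues, and 11 if it stops.

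**Reading A: 2+ means exactly 2+.** Every IHC value is the constant 2, and q is the RT-qPCR value.

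- Correlation = cov / (sd_IHC × sd_q) = 0/0, undefined.
- Consistency ICC = 2·cov / (var_IHC + var_q) = 0 / var_q = 0, whatever the true relation.
- Bland-Altman: difference d = q − 2 and mean m = (q + 2)/2, so d = 2m − 4. The slope is 2 and the correlation is 1 by construction.

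**Reading B: 2+ is a minimum and 3+ also qualifies.** The documents give no score distribution and no assay correlation, so all of the following are assumptions, shown as a range. Scores 0/1+/2+/3+ were split 20/30/30/20, 30/30/25/15 and 10/25/35/30. The latent EGFR/c-Met IHC correlation was 0.3, and the latent RT-qPCR/IHC correlation 0.5, 0.7 or 0.9. Both markers had to be 2+ or above. Power is for Spearman at two-sided 5%, n = 37.

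| Latent correlation | Spearman, full range | Spearman, 2+/3+ only | Power, full range | Power, 2+/3+ only |
|---|---|---|---|---|
| 0.5 | 0.46 | 0.26–0.30 | 0.81–0.84 | 0.31–0.42 |
| 0.7 | 0.65–0.66 | 0.40–0.45 | 0.99–1.00 | 0.71–0.82 |
| 0.9 | 0.85–0.86 | 0.64–0.69 | 1.00 | 1.00 |

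The variation lost can be checked by hand for the 20/30/30/20 split. Full-range variance about the mean of 1.5 is 0.4 × 2.25 + 0.6 × 0.25 = 1.05. Among eligible patients 45% score 3+, so the variance is 0.45 × 0.55 = 0.25, about 24% of the full value.

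A separate simulation (400,000 draws, latent correlations 0.5 and 0.7, four ordered classes) gave 0.47 falling to 0.26 and 0.66 falling to 0.42. Fisher-z power is Φ(√(n − 3) × atanh r − 1.96), with √34 = 5.831 at n = 37:

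- r = 0.47: Φ(2.974 − 1.96) ≈ 0.84. r = 0.26: Φ(1.552 − 1.96) ≈ 0.34.
- r = 0.66: Φ(4.623 − 1.96) > 0.99. r = 0.42: Φ(2.611 − 1.96) ≈ 0.74.

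At n = 11 (√8 = 2.828), r = 0.26 gives a power of about 0.12, counting both tails.

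**What is common to A and B.** No enrolled patient scores 0 or 1+ on either marker, so the lower part of the relation is unobserved.

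**The case against.** The strongest reply is that the wording points to a minimum. Criterion 3 speaks of overexpression, the background targets tumors overexpressing both receptors, and 6.6 looks for high transcript levels; leaving out 3+ tumors would sit oddly with all three. On that reading there is IHC variation, and good agreement would still show: at latent correlation 0.9 the restricted Spearman is 0.64–0.69 with power near 1.00. This stands. A reader might infer that no statistic could estimate the relation, or that little association would appear even if the assays agree well. The first holds only if 2+ is exact and the baseline eligibility score is the measure meant. The second fails under the 2+/3+ reading.

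A second reply is that the only IHC item among the listed correlatives (3.1.3) is phosphoprotein, which eligibility does not fix. That is correct for phosphoprotein, but 6.6 separately plans c-Met and EGFR expression by both RT-qPCR and immunohistochemistry, so the problem remains for total receptor. Post-treatment staining, mentioned in 6.6, does not clearly help: the schedule collects tissue only at screening.

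Three further inferences should not be drawn.

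- **Cox model.** Any effect there is limited to the baseline total-receptor score, which 3.1.3 does not list for correlation with PFS; only a broad reading of all biomarkers in 8.10 brings it in.
- **Number screened.** Dividing 37 by 0.30 gives about 123, but this applies an RT-qPCR prevalence to an IHC gate. The 3% TCGA figure in the same section would give about 1,233. Neither is a usable estimate.
- **Loss of screening scores.** The text discards samples; it does not say that results are discarded.

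**Conclusion.** The concern holds in limited form. Selection on IHC removes all of the variation in the baseline total-receptor score if 2+ is exact, and much of it if 3+ also qualifies. Under either reading, agreement across the expression range cannot be assessed from enrolled patients alone. That conclusion follows from the text and needs no assumption beyond the comparison using the total-receptor score. The size of the attenuation under the 2+/3+ reading rests wholly on assumed distributions and correlations: it is substantial when the true relation is moderate and does not prevent detection when it is strong. Phosphoprotein IHC is not affected in this way. No eligibility decision, stopping rule, primary test or safety analysis depends on this comparison.

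**What to change.** 1. In 8.10, name the IHC measure to be compared, and state in 5.1 and 6.6 whether 2+ is exact or a minimum.
2. Reconcile the use of RT-qPCR to find candidates in 6.6 with the eligible-only rule in 6.6 and footnote 8.
3. Amend 6.6 and footnote 8 so that IHC scores, and any RT-qPCR results already produced at screening, are kept and analysed for all screened patients under the existing screening consent (6.2). Leftover tissue is still discarded, which fits the no-banking rule in 10.5.
4. Report rank association in patients with both results, and the proportion co-expressing by each assay with exact intervals. State how many patients had only one assay, because using RT-qPCR as a triage step would restrict the range on that side instead.
5. If RT-qPCR is not done on ineligible patients, drop the agreement analysis and only describe RT-qPCR levels within the IHC-selected group.

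New RT-qPCR on screen failures should not be required. It is extra laboratory work on archival tissue that may be scarce, since fine-needle cores are accepted and KRAS is tested only where tissue is adequate.

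The cost is protocol and consent wording, with IRB approval of the amendment, and a little more analysis.

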3.1.3 Correlative Objectives

The following tests will be performed on blood and tumor tissue samples collected during this trial to correlate with PFS and OS:

- c-Met and EGFR mRNA by RT-qPCR
- plasma HGF and soluble Met receptor
- c-Met and EGFR phosphoprotein levels by IHC
- KRAS mutation status

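### Section 8.10 applies Bland-Altman plots and intra-class correlation to mRNA versus IHC, which share no scale, so the result is set by the arbitrary qPCR unit

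*Combined protocol and SAP*

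**What the plan says.** Section 8.10 (Correlative Analysis) plans that RT-qPCR levels of c-Met and EGFR "will be compared to c-Met and EGFR biomarkers as determined by IHC using Bland-Altman plots and intra-class correlation measures". Section 3.1.3 confirms that the RT-qPCR quantity is mRNA. Section 8.10 does not say which IHC variable is meant, and other sections leave several candidates:

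- **Eligibility score.** Section 5.1, criterion 3: "The subject must have EGFR and c-Met overexpressed in tumor as determined by immunohistochemistry (IHC) test score of 2+ for both markers".
- **Expression, readout not stated.** Section 6.6: "we will analyze tumor tissue to assess expression of c-Met and EGFR by RT-qPCR and immunohistochemistry".
- **Phosphoprotein.** Section 3.1.3 and the Synopsis list "c-Met and EGFR phosphoprotein levels by IHC". Section 6.6, however, gives phosphoprotein to another assay: "to evaluate Met and EGFR total phosphoprotein levels by electro-luminescent 2-site immunoassays in tissue".

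Section 6.6 also fixes who contributes data: "only patients with a test score of 2+ for both markers will be eligible to participate in this trial", and "Tissue samples collected from ineligible patients during screening will be discarded". Nowhere are mRNA and IHC converted to a common scale.

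**The concern.** A Bland-Altman plot shows the difference between two measurements of the same thing. Transcript abundance minus a staining result is not a quantity, so its mean and limits of agreement cannot be interpreted. An ICC compares between-patient variance with disagreement between methods, and that also needs a shared unit. RT-qPCR has no natural unit: Ct, delta-Ct, fold change and a logarithm to any base are all possible reports of the same assay.

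The underlying question is a real one for this trial. Section 2.2 takes its figure of about 30% co-expression from RT-qPCR, Section 6.6 would use rapid RT-qPCR to "consider these patients as candidate for the clinical trial, even before performing the more sophisticated studies", and enrolment itself rests on IHC. Whether mRNA tracks IHC is worth knowing. The danger is that a near-zero ICC produced by the choice of unit is read as discordance between the assays, or a high one as concordance.

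**Working it through.** The plan states no figure here to reproduce. The check asks whether the planned statistics depend on the qPCR unit.

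**1. Algebra.** Let the two methods have SDs s1 (qPCR) and s2 (IHC), correlation r and mean difference d. Then

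- consistency ICC = 2·r·s1·s2 / (s1² + s2²)
- absolute-agreement ICC ≈ 2·r·s1·s2 / (s1² + s2² + d²), ignoring a term of order 1/n.

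The correlation r is unchanged by a linear change of unit. The SD ratio and d are not. With r = 0.7 the consistency ICC is 0.70 at SD ratio 1, 0.56 at ratio 2, 0.14 at ratio 10 and 0.014 at ratio 100. With perfect correlation, ratio 100 still gives 2·100/(1 + 10,000) = 0.02.

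**2. Same data, three log bases.** Only n = 37 comes from the protocol (Section 8.5). Assumed: latent mRNA-protein correlation 0.95; IHC 0 to 3 in equal quarters of the protein latent; qPCR mean 6 and SD 2 in log2 units; patients with IHC 2 or more analysed.

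- The selected half of the protein latent has mean 0.798 and variance 0.363.
- The qPCR mean becomes 6 + 2·0.95·0.798 = 7.52, and its SD becomes 2·√(0.9025·0.363 + 0.0975) = 1.305.
- IHC has mean 2.5 and SD 0.5.
- The latent means in the score-2 and score-3 groups are 0.325 and 1.271, so the covariance of standardised qPCR with the score is 0.95·0.25·(1.271 − 0.325) = 0.225, and r = 0.225/(0.652·0.5) = 0.69.
- Multiplying by 0.693 gives ln units; multiplying by 0.301 gives log10 units.

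| Unit | s1 | d | Absolute ICC, formula | Consistency ICC, formula |
|---|---|---|---|---|
| log2 | 1.305 | 5.02 | 0.899/(1.702+0.25+25.16) = 0.03 | 0.899/1.952 = 0.46 |
| ln | 0.904 | 2.71 | 0.623/(0.818+0.25+7.34) = 0.07 | 0.623/1.068 = 0.58 |
| log10 | 0.393 | −0.24 | 0.271/(0.154+0.25+0.056) = 0.59 | 0.271/0.404 = 0.67 |

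Simulation at n = 37 (3,000 data sets) gives absolute 0.03, 0.07, 0.59 and consistency 0.47, 0.59, 0.67, with Spearman about 0.72 in all three. The column d is the Bland-Altman bias: it even changes sign with the log base.

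**3. Shifting the assumed qPCR mean** (log2 SD 2, means 0/2/4/6/8):

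- IHC 2 or more: absolute ICC 0.31/0.31/0.08/0.03/0.02; consistency 0.47 and Spearman 0.72 throughout.
- Unselected patients: absolute ICC 0.52/0.72/0.34/0.15/0.08; consistency 0.75; Spearman 0.90.
- Widening the SD to 1 to 3 with IHC 2 or more: absolute 0.01 to 0.61; consistency 0.34 to 0.67.

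**4. A second model** (latent correlation 0.7, log2 SD 1.5, IHC cut at −1, 0 and 1 SD, scores 0 to 3) compares qPCR reporting units on identical data. Absolute ICC is 0.34 on log2, 0.17 on log10, 0.41 as linear fold, 0.003 as fold × 100 and −0.12 as delta-Ct. The size of Spearman's correlation is 0.64 in every unit.

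**5. No variation in IHC.** If 2+ means exactly 2, r·s2 = 0, so both ICCs are 0 whatever the assays do. The Bland-Altman difference is then qPCR minus a constant, and correlates 1.0 with the plotted mean. No correlation can be estimated.

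**The case against.** The best case on the other side concerns weight rather than arithmetic. The cross-assay comparison is not a listed objective: Section 3.1.3 aims at correlation with PFS and OS, which is handled separately. No endpoint, eligibility decision or stopping rule uses the ICC, and Section 8.1 allows additional exploratory analysis and changes to the analysis plan without amendment unless a significant feature changes. That is correct and limits the stakes. It is also true that Section 8.10 does not itself tie the comparison to the 30% figure or to candidate selection; that link is an inference.

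Second, the section is silent on transformation, and an ICC on standardised values would behave well (0.69 against Spearman 0.72 in the example). But standardisation is not planned, it forces the Bland-Altman bias to zero, and it turns the ICC into roughly a correlation, which may as well be reported directly.

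Third, reading 2+ as excluding 3+ is strained when the criterion is overexpression, so the zero-variation case is only conditional. Truncation is not certain either. Section 6.6 mentions post-treatment immunostaining and Cycle 1/Day 15 tissue, which need not score 2+, although the Section 6.1 schedule collects tissue only at screening. If phosphoprotein is the variable, eligibility does not truncate it directly.

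Fourth, the immunostaining procedures and Laboratory Manual are not available here. Section 6.6 cites the manual for collection, processing, transfer and storage, not for scoring or statistics.

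Finally, the numbers are illustrative, and a latent correlation of 0.95 flatters the replacement. With IHC 2 or more, Spearman falls to 0.49 at latent 0.8 and 0.25 at 0.5. This stands and should be disclosed. None of these points makes the agreement statistics suitable.

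**Conclusion.** The concern holds. Applied as written, the Section 8.10 comparison has no interpretable Bland-Altman difference, and its ICC is governed by the qPCR unit. That follows from the formulas and needs no assumption about the assays. The size shown, 0.03 to 0.59 for the absolute-agreement ICC from a change of log base alone with Spearman fixed at about 0.72, rests on assumed inputs and predicts nothing about this trial's data. The 37 patients are reached only if stage 1 passes. The undefined IHC variable compounds the problem, but by itself would be missing detail rather than a wrong method. The consequence is confined to a correlative analysis; the change is worth making because it is cheap and prevents a misleading statement about assay concordance.

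**What to change.** Revise Section 8.10 as follows:

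1. Name the IHC variable compared (eligibility expression score or phosphoprotein), state whether 2+ includes 3+, and state the qPCR scale. Reconcile the phosphoprotein assay between Sections 3.1.3 and 6.6.
2. Replace Bland-Altman plots and ICC with Spearman's correlation or Kendall's tau-b with a 95% CI, and plot RT-qPCR level by IHC category.
3. If the eligibility score is used, state that range restriction attenuates the estimate and limits it to IHC-selected patients.
4. If IHC does not vary among those enrolled, report RT-qPCR levels descriptively.

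The analysis change is confined to wording in Section 8.10, with no new assay, sample or visit. The price is that a rank correlation shows association, not interchangeability. It is also weakened by selection (at latent 0.5, 0.45 unselected against 0.25 with IHC 2 or more) and is undefined if all scores are equal.
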